3. STUDY DESIGN

This will be a randomized, efficacy assessor-blinded, parallel group, pilot study of up to 20 subjects with documented UV induced herpes labialis. We will enroll until we have 20 subjects that have expressed a lesion from the induction and complete the treatment period of the study. With the possibility of screen failures and induction failures, we may consent up to 35 patients maximum.

Potential subjects will be assessed during a screening visit that must take place no greater than 2 weeks prior to the Induction visit. During the screening period, subjects that meet all other entry criteria will undergo UV susceptibility testing to determine their individual MED (minimal erythema dose). UV susceptibility testing takes place over two days with exposure to UV light on specified regions on the subject's back followed by an assessment of the exposed areas 24 hours later to identify the MED.

Subjects who have a measurable MED will be allowed to enroll in the study. Each subject will be randomly assigned in a 1:1 ratio to receive either EED or Comparator.

Subjects that do not have a measurable MED will be considered screen failures or may have repeat MED testing with new values.

At the Induction Visit, subjects will undergo UV radiation at a level 3 times their MED. The exposed area of the lip will be marked with indelible ink and a baseline photograph may be taken.

Each subject will then be randomly assigned in a 1:1 ratio to receive either EED or Comparator. Subjects will be dispensed study medication and instructed how to apply it to the exposed area. Dosing of the study product will be done 5 times daily, beginning at the time that a subject first senses the start of the prodromal phase (Day 1). The EED is a clear viscous eye drop, and the Comparator is a white cream substance. Therefore, the subject and principal investigator will be unblinded, and only efficacy assessments will be done by a qualified trained blinded assessor.

Subjects will be given a diary card to record their pain levels (starting at Day 1), progression of lesion development and any unusual symptoms (not normally seen with their outbreaks).

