4.3 Randomization Codes

A simple randomization code will be generated by the Investigator so that subjects are randomly assigned in a 1:1 ratio to either EED or Abreva.

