8.2 Independent Safety Review

An independent clinician will be assigned to review all available safety assessments on subjects as soon as 5 subjects reach EOS. This reviewer will be blinded to study treatment unless a safety concern is raised that requires identification of the subject's treatment group. Each subsequent safety evaluation will be conducted as 5 more subjects reach EOS and will include all available information from all subjects that have reached at least EOS. In other words, with each group of 5 subjects, the total reviewed will increase by 10 until all 20 subjects are included in the final independent safety evaluation.

The independent clinician will advise the Principal Investigator of any safety concerns or trends that could be a reason to terminate a specific subject's participation or to stop the study until it is deemed safe to continue.

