9. STATISTICAL METHODS

9.1 Analysis Populations

Analysis populations are defined as follows:

- The Safety population will include all subjects who use EED or Abreva for at least one day.
- The Per Protocol population will include all subjects (that were not induction failures) who complete the study, defined as attending all study visits.

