9.3 Safety Analysis

The safety analysis will be conducted on the Safety population.

Collection of AEs will begin on the first day of treatment and will be reported in simple per-subject listings.

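### No planned safety output compares EED with Abreva: the independent safety reviewer is blinded by default (section 8.2) and adverse events are only listed subject by subject (section 9.3)

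*Combined protocol and SAP*

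**What the plan says.** Section 8.2 assigns an independent clinician to review cumulative safety data each time 5 more subjects reach end of study. The clinician advises the principal investigator on concerns and trends that could end a subject's participation or halt the study. On access to treatment: "This reviewer will be blinded to study treatment unless a safety concern is raised that requires identification" of the individual subject's group.

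Section 9.3 is the whole safety analysis. It uses the Safety population, and its reporting rule is: "Collection of AEs will begin on the first day of treatment and will be reported in simple per-subject listings". Section 9.1 defines that population across both products: "The Safety population will include all subjects who use EED or Abreva for at least one day". Neither section specifies a count, percentage or interval by arm. Section 9.2 does compare the arms, but only for efficacy.

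Section 3 explains who knows the arm, given that the two products look different: "Therefore, the subject and principal investigator will be unblinded, and only efficacy assessments will be done by a qualified trained blinded assessor". Allocation is 1:1 (section 3), and section 4.3 describes the method: "A simple randomization code will be generated by the Investigator so that subjects are randomly assigned in a 1:1 ratio". No blocking is stated.

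**The concern.** The title promises a preliminary look at the safety of EED against an active comparator. The two places where that look could happen are the interim review and the final safety analysis. As written, neither sets one arm beside the other.

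At the interim reviews, the independent clinician is asked to find trends but does not see the variable along which the most informative trend would run. The route to the treatment group opens once a concern has been raised, and its wording refers to the individual subject's group. It therefore reads as a case-level code break and not as a view by arm. A serious or strange event would prompt it. A run of mild events, such as local irritation, need not, even if nearly all fell on one product.

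At the end, a listing gives no rate and no measure of uncertainty, so a reader must count by hand and cannot see how little about 10 subjects per arm can exclude.

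**Working it through.** The plan states no adverse event rate and no safety calculation, so there is no figure to reproduce. All event rates and arm splits below are assumptions.

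**1. Which planned outputs compare the arms.** Section 9.2: yes, for efficacy. Section 8.2: no, the reviewer is blinded by default. Section 9.3: no, per-subject listings. So no planned safety output does.

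**2. Effect of pooling on a rate.** Let s be the EED share, pE the EED rate and pC the Abreva rate. The pooled rate is s × pE + (1 − s) × pC.
- s = 0.5, pC = 0: pE = 20% pools to 10%, and 40% pools to 20%, exactly half.
- s = 0.5, pC = 10%: pE = 30% pools to 0.5 × 30% + 0.5 × 10% = 20%, which is 0.67 of the EED rate.

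**3. How firm the even split is.** Reading section 4.3 as unrestricted allocation, the number on EED is Binomial(N, 0.5).
- N = 20: the central 95% range is 6 to 14, and an exact 10/10 split has probability 17.6%.
- N = 10: a 5/5 split has probability 252/1024 = 24.6%, and the range is 2 to 8.
- N = 5 (first review): all five are in one arm with probability 2/32 = 6.25%.

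A blinded reader therefore lacks the denominators as well as the labels.

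**4. What an unlabelled list cannot separate.** Reviews in steps of 5 give cumulative totals of 5, 10, 15 and 20. (Section 8.2 also says that the total rises by 10 with each group of 5; the two statements must be reconciled.) Take the second review with an assumed 5/5 split and 4 affected subjects:
- 4/5 v 0/5: two-sided Fisher p = 2 × C(5,4) × C(5,0) / C(10,4) = 2 × 5/210 = 0.048.
- 2/5 v 2/5: p = 1.0.

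The p-values serve only to show how different the two situations are. Without arm labels both read as 4 of 10.

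**5. What pooling does not hide.** Assume an EED rate of 20%, none on Abreva. The chance of at least one event is 1 − 0.8^10 = 89% among 10 EED subjects, and 1 − 0.9^20 = 88% among 20 subjects with a pooled rate of 10%. Events are seen almost equally often. The rate and the attribution to an arm are lost.

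**6. What a by-arm table could and could not do.** With 10 per arm and no comparator events, two-sided Fisher p is 0.21 for 3/10, 0.087 for 4/10 and 0.033 for 5/10. Power at the 5% level is 15%, 37%, 62% and 83% for true EED rates of 30%, 40%, 50% and 60%. For 0 events in 10, the exact two-sided 95% upper limit is 1 − 0.025^(1/10) = 30.8% (one-sided: 1 − 0.05^(1/10) = 25.9%). The table is useful as description, not as a test.

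**The case against.** The other side has a good deal to say, and much of it stands.

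- **The objective and safety endpoint name no comparator.** Section 2 asks for preliminary data on EED, and section 2.2 simply names adverse events. This stands: the comparative safety claim rests on the title alone. The title is still a public statement of what the study assesses.
- **Other eyes are on safety.** The principal investigator knows the arm, staff check diaries for adverse events at visits, and serious events go to the manufacturer within 24 hours. An investigator who sees a pattern can raise a concern and so open the route in section 8.2. This stands, and it limits the harm. But no by-arm summary is specified for the investigator either, and an impression at the site is not the independent review that the plan describes.
- **Four of 10 might itself count as a concern.** If four subjects had the same event, the reviewer could well ask for the arm. This is fair for a striking event. It is weaker for four mild, differing or expected events.
- **Blinding has a purpose.** It keeps judgement of individual cases free of knowledge of the product. Coded arms largely keep that protection.
- **The listings may show treatment.** Section 9.3 does not say that they omit it, and about 20 subjects can be counted by hand. This stands, but leaves the comparison to the reader.

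A reader might go further and infer that a harm confined to EED would go unseen, or would always appear at half its rate. The documents do not support this: single events remain visible, the treatment group can be identified, and halving needs an even split and no comparator events. Nor do they support calling the trial open-label or saying that it compares the arms on nothing: efficacy is rated by a blinded assessor and compared by arm.

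**Conclusion.** The point holds in a limited form. Sections 8.2 and 9.3 together leave the plan without any safety output that sets EED beside Abreva. The gap is in attribution and rate, not in detection of single events. Its size depends on assumptions that the documents do not settle: a pooled rate averages half the EED rate with an even split and no events on Abreva, and about two thirds of it with 30% on EED and 10% on Abreva. Unrestricted allocation adds uncertainty about the denominators.

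The wide upper limit for zero events, 30.8% with 10 subjects, comes from the sample size. A reader might take it as a fault that better reporting would cure. It is not: an interval shows that limit but does not lower it.

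This is a cheap improvement to a small pilot, not a flaw that undermines it.

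**What to change.** **Section 8.2.** Give the independent clinician each cumulative listing grouped by coded arm (A and B), with the number of subjects in each. Unblinded staff hold the code and open it on request.

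**Section 9.3.** Keep the listings. Add one table by arm, on the Safety population: number and percentage of subjects with any adverse event, each with an exact (Clopper-Pearson) 95% confidence interval. State that it is descriptive and that no test is planned. Add rows for related and for application-site events only if those attributes are recorded; sections 8.1.1 and 8.1.2 define neither a relatedness scale nor a coding scheme, so these rows would otherwise need new data definitions.

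**Cost.** A sort order, two denominators and one small table. The safety reviewer may guess which coded arm is EED. That affects no efficacy rating, because section 7.1 gives the rating of prodrome and lesions to a separate blinded assessor who does no safety evaluation.

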--	--

[figure not shown]
	have reached EOS. Thereafter, the independent safety evaluation will occur as each subsequent group of 5 subjects reaches EOS and will include data on all subjects having reached EOS.
Enrollment Period	Subjects will be enrolled over a 2 year period.
Treatment Period	Subjects will be treated for up to 7 days from the time they first experience a prodrome and/or a lesion. If lesion has not resolved by day 7, the maximum number of days the patient may use study drug treatment is 10 days. If subjects reach EOS without full resolution of their lesion(s), they will be given the option to begin taking a prn standard of care medication for the remainder of the outbreak. Subjects that do not exhibit a prodrome within 7 days of the induction visit, will be considered induction failures and be discharged from the study. Total time of study participation for any given subject may range from 13 to 25 days.
Location	University of Utah MidValley Clinic, Department of Dermatology
Safety Assessments	Solicited AEs by review of diary cards and discussion with subjects
Efficacy Assessments	Primary: 
Number of subjects that experience prodrome (Stage 1) but do not progress to vesicles (Stage 3) by completion of treatment Secondary: 
Subject-assessed duration of painClinician-assessed duration of lesion appearance (Stage 3), as reported by subject, to complete healing (Stage 5)Measurement of cumulative lesion area (all eruptions if more than 1)Measurement of each lesion (if more than one) from eruption (Stage 3) through healing of hard crust (Stage 4) to identify the largest lesion

TABLE OF CONTENTS

PROTOCOL SYNOPSIS	ERROR! BOOKMARK NOT DEFINED.
1. INRODUCTION	1
1.1 Background and Rationale	1
2. OBJECTIVE	2
2.1 Efficacy Endpoints	2
2.1.1 Primary:	2
2.1.2 Secondary:	2
2.2 Safety Endpoint	2
3. STUDY DESIGN	2
4. STUDY TREATMENT	4
4.1 EDTA Eye Drops	Error! Bookmark not defined.
4.2 Comparator: Abreva®	4
4.3 Randomization Codes	4
5. SUBJECT POPULATION	4
5.1 Inclusion Criteria	4
5.2 Exclusion Criteria	5
6. STUDY PROCEDURES	6
6.1 Study Visits	6
6.1.1 Screening Visit (Days -14 to 0)	6
6.1.2 Study Day 1 Visit (Baseline)	Error! Bookmark not defined.
6.1.3 Study Days 3 and 5 Visits	8
6.1.4 Study Day 7 +/- 1 day Visit	8
6.2 Study Day 10 Visit	Error! Bookmark not defined.
6.2.1 End of Study (EOS) Visit	Error! Bookmark not defined.
6.3 Early Discontinuation Visit	9
7. EFFICACY EVALUATIONS	9

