8.1.2 Evaluation and Reporting of Adverse Events

All AEs (i.e. a new event or an exacerbation of a pre-existing condition) that occur after the start of dosing and up to 2 after the EOS visit, will be recorded as an AE or SAE (if applicable). (Any event occurring prior to start of treatment on Day 1 will be recorded as part of the subject's medical history.) All subjects who have used the study product at least once will be evaluated for safety.

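### The independent safety reviews are limited to subjects who reached EOS, so dosed subjects who stop early may be in none of them; the stated step of 10 should also be 5

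*Combined protocol and SAP*

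**What the plan says.** Section 8.2 assigns an independent clinician to "review all available safety assessments on subjects as soon as 5 subjects reach EOS". Each later review is "conducted as 5 more subjects reach EOS and will include all available information from all subjects that have reached at least EOS". An explanatory sentence then restates the rule: "with each group of 5 subjects, the total reviewed will increase by 10 until all 20 subjects" are covered in the last review.

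The Design row of the synopsis gives the same trigger and the same restriction, without the figure of 10: "the independent safety evaluation will occur as each subsequent group of 5 subjects reaches EOS and will include data on all subjects having reached EOS".

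The protocol's other safety rules depend on exposure. Section 8.1.2 states: "All subjects who have used the study product at least once will be evaluated for safety". Section 9.1 puts anyone with at least one day of use into the Safety population. Neither requires the subject to reach EOS.

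Section 3 and Section 6.1.5 place EOS at full healing or Day 10, whichever is earlier. For subjects who leave early, Section 6.2 asks the site to try to obtain the EOS assessments. It does not say that these subjects then count as having reached EOS.

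**The concern.** The subjects most likely to fall outside a review built on EOS are those who stopped before it, and an adverse event is one reason to stop. The protocol foresees early exits: by the subject's own choice or the investigator's decision (Section 6.2), or because staff end participation for non-compliance (Sections 6.1.3 and 6.1.4). If the restriction is followed as written, the independent clinician could judge the safety of a product without seeing some of the people who tolerated it worst.

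The restriction also sits badly with the clinician's task. Section 8.2 expects advice on ending an individual subject's participation, but a subject who has reached EOS has essentially finished.

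The step of 10 is a smaller matter. It contradicts the sentence before it and leaves the size of each review package misstated.

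**Working it through.** **1. The increment.** Inputs are the first review at 5 subjects at EOS, later reviews at every 5 more, and a final total of 20 (Section 8.2). The cumulative number at review k is 5 × k:

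- k = 1, 2, 3, 4 gives 5, 10, 15, 20.
- The step is 5k − 5(k − 1) = 5. The plan states 10, which is not reproduced.

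Three other readings of the 10 were tried:

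| Reading | Totals | Why it fails |
|---|---|---|
| Start at 5, then add 10 | 5, 15, 25 | Never equals 20; needs 15 subjects when 10 are at EOS |
| Add 10 from zero | 10, 20 | Twice the 5 and 10 subjects at EOS at those reviews |
| Cumulative subject-reviews, summing 5k | 5, 15, 30, 50 | Steps after the first are 10, 15, 20; ends at 50 |

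No reading gives a step of 10 per group of 5 that ends at 20. A step of 5 does end at 20 and agrees with the rest of Section 8.2 and with the synopsis.

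**2. Coverage, side by side.**

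| Place | Who is covered |
|---|---|
| 8.2, first review | Available safety assessments on subjects; no express EOS limit |
| 8.2, later reviews | Subjects who have reached at least EOS |
| Synopsis, Design | Subjects having reached EOS |
| 8.1.2 | Anyone who used the product at least once |
| 9.1, Safety population | Anyone with at least one day of use |
| 6.2, early discontinuation | EOS assessments sought; status as having reached EOS not stated |
| 8.1.4, SAEs | To the manufacturer within 24 hours and to the IRB; independent clinician not named |

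A dosed subject who leaves and does not complete the EOS assessments meets the exposure rules in 8.1.2 (and in 9.1 after a day of use). The same subject does not meet the EOS rule for the later reviews. No other section brings that subject back into a review.

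**3. How many subjects.** Section 5 enrols until 20 subjects have expressed a lesion and completed the treatment period, so early stoppers come on top of those 20. The documents give no dropout rate. For an assumed fraction d of dosed subjects stopping early, the number dosed is 20 / (1 − d), rounded up:

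| d (assumed) | 20 / (1 − d) | Dosed | Beyond the 20 |
|---|---|---|---|
| 5% | 21.1 | 22 | 2 |
| 10% | 22.2 | 23 | 3 |
| 15% | 23.5 | 24 | 4 |
| 20% | 25.0 | 25 | 5 |

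These are upper figures under each assumption, because some early stoppers will complete the EOS assessments and may be counted.

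**The case against.** Several points narrow the gap. The sentence on the first review has no express EOS limit. The synopsis says an independent physician evaluates safety over the whole course of the study. Section 6.2 seeks EOS assessments from early stoppers, so many may be counted in practice. The clinician's power to advise on an individual's participation suggests that a wider view was intended. Section 8.1.2 governs the recording and evaluation of adverse events rather than the interim review, so it does not strictly contradict Section 8.2. Subjects still on treatment reach EOS by Day 10 if they stay, and then enter a later review.

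All of this stands as evidence of intent, and it makes the coverage ambiguous. It does not override two explicit statements that the data come from subjects who have reached EOS, and no section counts an early stopper as one of them.

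A reader might infer more than the documents support:

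- **That the step of 10 halves the number of reviews.** It does not. Timing is set by each further 5 subjects at EOS, which Section 8.2 and the synopsis both state. The 10 describes how many subjects are in a review, not when one takes place, so no review is skipped.
- **That early stoppers escape all outside oversight.** They do not. Their SAEs go to the manufacturer and the IRB under Section 8.1.4, and their adverse events are listed for the Safety population under Section 9.3. What they may lack is a place in the scheduled independent review.

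**Conclusion.** The coverage point holds and is the one that matters. As written, Section 8.2 and the synopsis do not guarantee that dosed subjects who stop early without EOS assessments are seen in any independent review. The possible extent is about 2 to 5 subjects in addition to 20 completers. That range rests on an assumed 5% to 20% early-stopping rate and on none of those subjects being counted as having reached EOS; the plan supplies neither figure.

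The increment is wrong on every reading tried and should be 5. On its own this is close to clerical, because the review schedule is clear and workable. Neither part affects the sample size or the efficacy analysis.

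**What to change.** Keep the trigger at each fifth subject reaching EOS. In Section 8.2 and in the synopsis, state that each review includes all available safety data on all subjects dosed to date, including early discontinuations and those still on treatment. This brings the review into line with the exposure-based rules in Sections 8.1.2 and 9.1.

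In the explanatory sentence of Section 8.2, change the step from 10 to 5. Add that the totals 5, 10, 15 and 20 count subjects at EOS, and that early discontinuers are additional to the 20 completers.

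The cost is a short wording change in two places and a few more listings for the reviewer at each look.

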9. STATISTICAL METHODS

9.1 Analysis Populations

Analysis populations are defined as follows:

- The Safety population will include all subjects who use EED or Abreva for at least one day.
- The Per Protocol population will include all subjects (that were not induction failures) who complete the study, defined as attending all study visits.

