5. SUBJECT POPULATION

We will enroll until we have 20 subjects that have expressed a lesion from the induction and complete the treatment period of the study. With the possibility of screen failures and induction failures, we may consent up to 35 patients maximum.

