6.1.2 Induction Visit

Upon reporting to the clinic for their induction visit, the subject will be randomized to receive either EED or Abreva. The following assessments will then be performed to establish baseline values prior to dosing:

- Review of Medical History and Concomitant Medications for any changes between Screening and Day 1 (Treatment emergent AEs are collected in this study beginning with first instance of dosing. Any unusual symptoms prior to the start of dosing will be recorded, if appropriate, as an update to the subject's medical history).

- Limited Physical Exam to check for any changes between Screening and Day 1(changes in PE after start of dosing will be assessed as possible treatment emergent AEs)

If the subject remains qualified for the study:

- They will be dispensed study product (EED or Abreva) and instructed to use it 5 times daily beginning when they first sense a prodrome or see a lesion (they will be asked to note the day and time of their first dose on their diary card).
- They will be given a diary card and instructed how to complete it. A practice diary completion may be done to ensure that subjects know how to complete the diary.

Subjects will then be discharged from the clinic with an appointment to return on Day 3 via virtual video call. They will be instructed to bring their Diary Card and the tube/bottle of study product that they have received.

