6.2 Early Discontinuation Visit

If at any time during the study, a subject wants to stop participating or the Investigator believes it is in the subject's best interest to stop treatment, every effort should be made to complete the final assessments noted in the EOS visit.

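### Section 9.1 requires a day of product use for the Safety population, without defining a day, while Section 8.1.2 requires one use; a subject who stops within hours may be missing from the adverse event listings

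*Combined protocol and SAP*

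**What the plan says.** Three places in the combined protocol and SAP decide who counts for safety.

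- Section 8.1.2, on recording adverse events: "All subjects who have used the study product at least once will be evaluated for safety".
- Section 9.1, on analysis populations: "The Safety population will include all subjects who use EED or Abreva for at least one day".
- Section 9.3, on the analysis itself: "The safety analysis will be conducted on the Safety population".

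Section 9.3 also fixes the output: "Collection of AEs will begin on the first day of treatment and will be reported in simple per-subject listings". Section 6.1.2 gives the start of collection: "Treatment emergent AEs are collected in this study beginning with first instance of dosing".

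No section defines a day of use, and none says which of the two thresholds prevails.

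**The concern.** The plan collects adverse events from the first application. On the plain wording of Section 9.1, it then analyses only subjects whose use lasted a day. Someone who applies the product once or a few times, has a local reaction and stops would meet the Section 8.1.2 threshold but might not meet the one in Section 9.1. Such an exclusion can depend on the outcome being studied, because poor tolerability is an obvious reason to stop within hours.

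Preliminary safety is part of the study's single objective (Section 2). The test product is an eye drop containing a permeation enhancer (Section 4.1), used here on lip skin irradiated at three times the MED (Section 3), so early local tolerability is a reasonable thing to look for. The only other analysis set, Per Protocol, requires attendance at all visits. The Safety population is therefore the only defined set that could hold this subject.

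**Working it through.** The plan gives no figure to reproduce here, so the check is mainly a comparison of texts.

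**1. Can such a subject arise?** Yes. Section 3 sets the regimen in a sentence that opens: "Dosing of the study product will be done 5 times daily, beginning at the time that a subject first senses the start of the prodromal". A subject can therefore have between one and four applications and stop before completing a day's regimen. Section 6.2 foresees that use may end early, and asks staff to try to complete the EOS assessments when it does. Its sentence opens: "If at any time during the study, a subject wants to stop participating or the Investigator believes it is in the subject's best interest to".

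**2. Who is in the Safety population under each reading of a day?**

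| Subject's use | 9.1 as a full elapsed day | 9.1 as a day's five applications | 9.1 as any use on Day 1 | 8.1.2 |
|---|---|---|---|---|
| One application, then stops | out | out | in | in |
| Four applications, stops the same day | out | out | in | in |
| Five applications in one day, then stops | out | in | in | in |
| Starts in the evening of Day 1 and continues | in | in | in | in |

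Only the third reading agrees with Section 8.1.2 in every row. Two analysts could classify the first three subjects differently, and could do so after seeing the data.

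**3. What does the loss consist of?** Section 9.3 plans per-subject listings only. It plans no incidence, denominator or between-arm test. The possible loss is one subject's entry and an exposed count that is one too low.

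**4. Illustration of scale.** The inputs are the target and the 1:1 ratio (Section 4.3). The target is: "We will enroll until we have 20 subjects that have expressed a lesion from the induction and complete the treatment period of the study". An early stopper does not complete treatment and so is additional to the 20.

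- Assume an even split: 20 / 2 = 10 completers per arm. Simple randomization does not guarantee this.
- Assume one early stopper in one arm, who has that arm's only reaction.
- Stopper included: 1 / (10 + 1) = 1/11 = 9.1% (exact 95% interval 0.0023 to 0.4128).
- Stopper excluded: 0/10 = 0% (exact 95% interval 0 to 0.3085).

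The intervals overlap almost entirely. What differs is whether the event is seen at all.

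**5. How likely is one such subject?** The documents give no rate, so an assumed rate p is varied. The chance of at least one early stopper among 20 treated subjects is 1 − (1 − p)^20:

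- p = 2%: 33.2%
- p = 5%: 64.2%
- p = 10%: 87.8%
- p = 20%: 98.8%

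These figures show only that the case cannot be dismissed at modest rates. They do not estimate how often it will occur.

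**The case against.** The strongest reply is that the exclusion is not established. The Design row of the synopsis makes Day 1 the day on which the subject senses a cold sore and applies the product. Section 8.1.2 places the start of treatment on Day 1, and Section 9.3 starts collection on the first treatment day. The plan thus counts days from first use, and one application on Day 1 can be read as one day of use. Requiring five applications on Day 1 itself would also be odd, because a fully compliant subject whose prodrome begins in the evening would fall short that day. This stands. A reader might infer that early stoppers are certainly dropped, but the documents support only that they may be. The duration reading is still the more natural one, and Section 8.1.2 shows that the authors could specify a single use when they meant it.

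A reader might also infer that a reported incidence would fall from 1/10 to 0/9. Section 9.3 reports no incidence, and those denominators count the early stopper among the 20 completers, contrary to the enrolment rule.

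A third tempting inference is that the safety data would be lost, or that the worse-tolerated product would be favoured in a comparison. Neither is supported. Section 8.1.2 records every event after dosing starts, and Section 8.1.4 requires serious events to go to the manufacturer and the IRB. The independent review in Section 8.2 is not tied to the Section 9.1 set. That review does cover subjects who have reached EOS, and Section 6.2 asks only for best efforts to complete the EOS assessments of someone who stops early, so it may not pick the subject up. No between-arm safety test exists to be biased.

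**Conclusion.** The point holds as an inconsistency between Sections 8.1.2 and 9.1 that turns on an undefined term, with Section 9.3 making the Section 9.1 wording decisive. On the duration reading, a subject who stops within hours is absent from the safety listings and the exposed count. On the Day 1 reading, nothing is lost. The severity is minor to moderate: data collection and serious event reporting are unaffected, and no test or planned rate changes. It is still worth correcting, because in a pilot of about 20 completers the individual listings are the safety result, and the subject at risk of omission is the one most likely to show early intolerance. The conclusion about the text needs no numerical assumption. The 1/11 against 0/10 contrast assumes an even split and a single early stopper, and the frequency of such subjects is unknown.

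**What to change.** In Section 9.1, replace the requirement of a day's use with at least one use, so that the Safety population is all subjects who applied EED or Abreva at least once. This matches Section 8.1.2 and the first-dose start of collection in Section 6.1.2, and it removes the need to define a day of use. If the sponsor already meant any use on Day 1, the change only makes that explicit.

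The cost is one phrase. Subjects already note the day and time of their first dose on the diary card (Section 6.1.2), so no new data, visits or subjects are needed.
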